8.1 Definitions

Adverse Event

An **adverse event** (AE) is any symptom, sign, illness or experience that develops or worsens in severity during the course of the study. Intercurrent illnesses or injuries will be regarded as adverse events. Abnormal results of diagnostic procedures are considered to be adverse events if the abnormality:

- results in study withdrawal
- is associated with a serious adverse event
- is associated with clinical signs or symptoms
- leads to additional treatment or to further diagnostic tests
- is considered by the investigator to be of clinical significance

Serious Adverse Event

Adverse events are classified as serious or non-serious. A **serious adverse event** is any AE that is:

- fatal
- life-threatening
- requires or prolongs a hospital stay
- results in persistent or significant disability or incapacity
- a congenital anomaly or birth defect
- an important medical event

Important medical events are those that may not be immediately life threatening, but are clearly of major clinical significance. They may jeopardize the subject, and may require intervention to prevent one of the other serious outcomes noted above. For example, drug overdose or abuse, a seizure that did not result in in-

CONFIDENTIAL

patient hospitalization, or intensive treatment of bronchospasm in an emergency department would typically be considered serious.

All adverse events that do not meet any of the criteria for serious should be regarded as *non-serious adverse events*.

Adverse Event Reporting Period

The study period during which adverse events must be reported is normally defined as the period from the initiation of any study procedures to the end of the study treatment follow-up. For this study, the study treatment follow-up is defined as 30 days following the last administration of study treatment.

Preexisting Condition

A preexisting condition is one that is present at the start of the study. A preexisting condition will be recorded as an adverse event if the frequency, intensity, or the character of the condition worsens during the study period.

General Physical Examination Findings

At screening, any clinically significant abnormality will be recorded as a preexisting condition. At the end of the study, any new clinically significant findings/abnormalities that meet the definition of an adverse event will also be recorded and documented as an adverse event.

Post-Study Adverse Event

All unresolved adverse events will be followed by the investigator until the events are resolved, the subject is lost to follow-up, or the adverse event is otherwise explained. At the last scheduled visit, the investigator will instruct each subject to report any subsequent event(s) that the subject, or the subject's personal physician, believes might reasonably be related to participation in this study.

Hospitalization, Prolonged Hospitalization or Surgery

Any adverse event that results in hospitalization or prolonged hospitalization will be documented and reported as a serious adverse event unless specifically instructed otherwise in this protocol. Any condition responsible for surgery should be documented as an adverse event if the condition meets the criteria for an adverse event.

Neither the condition, hospitalization, prolonged hospitalization, nor surgery are reported as an adverse event in the following circumstances:

- Hospitalization or prolonged hospitalization for diagnostic or elective surgical procedures for a preexisting condition. Surgery should **not** be

reported as an outcome of an adverse event if the purpose of the surgery was elective or diagnostic and the outcome was uneventful.

- Hospitalization or prolonged hospitalization required to allow efficacy measurement for the study.
- Hospitalization or prolonged hospitalization for therapy of the target disease of the study, unless it is a worsening or increase in frequency of hospital admissions as judged by the clinical investigator.

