1.1 Background

Depression frequently emerges during adolescence and is associated with severe outcomes. Current interventions do not lead to remission for many adolescents. Treatment-resistant depression (TRD) in adolescence is an ominous prognostic indicator for a lifetime of suffering and increased risk for suicide. Efforts should be directed toward novel interventions that could alter this perilous course. Theoretically, restoration of healthy development during this critical window would substantially improve outcomes over the lifespan.

Ketamine is a noncompetitive, high-affinity antagonist of the *N*-methyl-D-aspartate type glutamate receptor that has long been used for induction and maintenance of anesthesia in children and adults, and recently has been investigated for its rapid antidepressant effects.

No results from any studies examining effectiveness of either single-dose or serial-dose ketamine have yet been published in adolescents with TRD. Because of the ongoing neurodevelopment in adolescence, which is thought to confer enhanced neuroplasticity, it is possible that adolescents with TRD could show greater responses and more sustained remission than adults with TRD. The biological mechanisms of depression impacted by ketamine are only now being uncovered in adults (Zarate et al., 2013). Characterization of the neural mechanisms underlying ketamine response or non-response in adolescents with TRD will represent a significant advance.

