4.3 Subject Recruitment and Screening

Adolescents with treatment resistant depression who have been admitted to the adolescent mental health inpatient unit, who present to the University of Minnesota Psychiatry Adolescent Mood Clinic, or who are referred from outside clinicians, and who meet inclusion and exclusion criteria for the study, will be invited to participate.

Prior to enrollment, project staff selected to recruit for this study will screen review records from the hospital and clinical services noted above to determine potentially eligible adolescent participants. If an adolescent appears to meet basic criteria for the study (appropriate age and diagnosis), staff will then check the consent for treatment form in the patient's chart. If parents indicated on that form their willingness to have their child's medical records used in research, study staff will then contact the current treating provider to determine whether the provider feels it would be appropriate to invite this participant into the study. If so, the provider will request written permission of the adolescent and/or the parent for the study staff to contact them regarding the study. The study staff will then contact the parents by phone or in person to inform them about the purpose and activities of the current study.

We anticipate that some families will hear about our study through word of mouth or by searching on ClinicalTrials.gov. We will post information about the study in the community using flyers and online posting boards.

If after hearing about the study from study staff patients/families are interested in participating, the study staff will then conduct a screening form to ensure eligibility. If parents are interested and the adolescent is eligible, the first study visit will be scheduled. Informed consent will be obtained at the time of the first study visit.

CONFIDENTIAL

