4.4 Early Withdrawal of Subjects

When and How to Withdraw Subjects

A subject may be withdrawn from the study prior to expected completion for the following reasons:

- Participant experiences adverse side effects to the ketamine treatments that are intolerable to the adolescent or the parent.
- Participant fails to adhere to protocol requirements
- Participant or participant's parent(s) withdraw consent

If a subject exits the study for any reason (withdrawal, non-response, or relapse), he or she will continue his or her pre-study regimens and consult with his or her psychiatrist about the next step in treatment.

Data Collection and Follow-up for Withdrawn Subjects

For all participants, we will request permission during the consent process to collect naturalistic follow-up data through in person visit to clinic or video conference 6 months after the 6-week study period.

The naturalistic follow-up encounter will be as follows:

We will ask permission to contact the family to inquire about the participant. Subjects will be determined lost to follow-up if they do not respond to 4 e-mails to the primary e-mail address of parent(s) or 4 phone calls to their primary number or to their next-of-kin, or to a certified letter.

During the follow up in person visit to clinic or video conference subject will be asked to provide:

- a) A narrative interval history including following elements
 - a. Changes in medications and their effects
 - b. Therapies or other treatments they have undergone and their effects
 - c. Evolution of their symptoms during the interval
 - d. Any hospitalizations including cause and outcome
 - e. Any suicide attempts including precipitating factor (if any) and outcome
- b) Participate in a clinical interview in order for clinician to complete an assessment using CDRS-R, CADSS, CGI, and MADRS.
- c) Complete the BDI-II, Profile of Mood States – Adolescent, SHAPS and TEPS

5 Study Drug

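### Section 8.1 lets admissions for depression that the investigator judges neither a worsening nor more frequent escape AE and SAE status, and conflicts with the same section's rule on pre-existing conditions

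*Combined protocol and SAP*

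**What the plan says.** The protocol's reporting rules for hospital stays are in section 8.1, under Hospitalization, Prolonged Hospitalization or Surgery. The exemption opens with "Neither the condition, hospitalization, prolonged hospitalization, nor surgery are reported as an adverse event in the following circumstances". Its third bullet reads "Hospitalization or prolonged hospitalization for therapy of the target disease of the study, unless it is a worsening", and goes on to a second exception that leaves the decision to one person: "increase in frequency of hospital admissions as judged by the clinical investigator". No criteria or reference point are given for either exception, and suicidality is not mentioned.

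Three other parts of 8.1 bear on this.
- An AE is something that arises, or becomes more severe, while the study is running.
- A pre-existing condition is recorded as an AE if it becomes more frequent, more intense or different in character. This rule has no investigator-judgement clause.
- An SAE is an AE that also meets a seriousness criterion, one of which is that it "requires or prolongs a hospital stay".

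On the population, section 1.1 calls treatment-resistant depression in adolescence "an ominous prognostic indicator for a lifetime of suffering and increased risk for suicide". Section 4.3 lists among those to be invited "Adolescents with treatment resistant depression who have been admitted to the adolescent mental health inpatient unit".

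**The concern.** In most trials an exemption for stays due to the disease under study keeps background events out of the safety tables. Here the disease is severe depression in adolescents, and admission for it, possibly for suicidality, is one of the serious outcomes a reader of the safety results will look for. The exemption removes the condition as well as the stay. Whether it applies is decided, without criteria, by the investigator of a single-arm, open-label study with a sponsor-investigator, so there is no control arm and no independent check on that decision.

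At stake is whether the SAE count can be read as the number of participants with a serious psychiatric event. An admission without AE status does not trigger the SAE form that section 8.2 requires within 24 hours. It is not among the SAEs that medical monitoring counts under 8.6, nor among the AEs that 8.6 says the safety panel will review, first after five participants have had at least one infusion and then annually.

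**Working it through.** The plan states no admission rate or expected SAE count, so there is no figure to reproduce. The check is a reading of the rules side by side, followed by a scale for n = 20.

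**1. Do the general rules restore what the exemption removes?**
- The default in 8.1, that an AE leading to hospitalization is an SAE, gives way where the protocol specifically instructs otherwise. The third bullet is such an instruction.
- The SAE definition does not restore it, because an SAE must first be an AE.
- The pre-existing-condition rule restores it only if the condition has worsened. The two parts of 8.1 then differ on how that is settled: one states it as a fact about the condition, the other makes it the investigator's judgement.

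**2. Which situations fall through?**

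| Situation | AE and pre-existing-condition rules | Third exemption bullet | Outcome |
|---|---|---|---|
| Outpatient, new or worse suicidality, admitted | AE | Worsening or more admissions should apply | Reportable, subject to the judgement |
| Enrolled as an inpatient, stay extended, symptoms as at entry | No clear worsening | Neither exception clearly met | Can be exempt |
| Improves, relapses to entry severity, admitted | Depends on whether the comparison is with entry or with the improved state | Same ambiguity; frequency depends on past admissions | Undetermined; can be exempt |

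The third row is foreseeable, since relapse is a defined secondary endpoint (section 3.3).

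**3. What else would capture such an admission?**
- AEs are asked about at each visit (6.3) and by specific questioning at each contact (8.2). The event would probably be heard of, but the exemption then decides whether it counts as an AE.
- The since-last-visit form of the Columbia suicide scale is named at Visit 10 (6.6). Section 6.7 says Visits 11-16 use the same assessments, yet its bracketed list omits that scale. Section 6.3 does not list it at infusion visits.
- The 6-month naturalistic contact (4.4) asks about hospitalizations with their cause, and about "Any suicide attempts including precipitating factor (if any) and outcome". This is late, depends on permission, and is a narrative history, not AE reporting.

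**4. Scale at n = 20 (section 3.1).** If all 20 are dosed, one participant is 1/20 = 5.0%.
- One admission reported: 5.0%, exact (Clopper-Pearson) 95% interval 0.1% to 24.9%.
- The same admission exempted: 0/20, interval 0% to 1 − 0.025^(1/20) = 16.8%.

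The chance of at least one admission for depression among 20 is 1 − (1 − p)^20, where p is the per-participant rate. For assumed p of 2%, 5%, 10% and 15% it is 33%, 64%, 88% and 96%. These rates are assumptions and cover any admission for depression. The share that would be judged exempt cannot be derived from the documents.

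**The case against.** The case for leaving the clause alone is substantial, and most of it stands.

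- **The second exception is wide.** A first admission of an outpatient, or a readmission, would ordinarily count as an increase in frequency. An admission is exempt only if neither exception is judged to apply.
- **Suicidality is not written into the exemption.** New or worse suicidality meets the AE definition and the pre-existing-condition rule. Life-threatening events and important medical events are serious without a hospital stay, and overdose is a named example. Treating suicidality as part of the target disease is an inference that the wording allows but does not state.
- **Some exemption is reasonable.** Inpatients may enrol, and a stay already under way at consent is not a study event.
- **Other channels exist**, as set out in step 3 of the working.

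A reader might go further and infer that psychiatric admissions, including those for suicidality, go unrecorded. The text does not support that: it says they are not reported as AEs, and other records of them may exist. A reader might also infer that exempted admissions are barred from the stopping rule, or that the exemption is what keeps them from the IRB and FDA. Section 8.5 has no event count and refers to new results in general. Section 8.3 reporting turns mainly on unexpectedness and relatedness, and includes a route to the IRB for unanticipated, related events that are not SAEs. The panel's remit also includes a general reassessment of risk and benefit, although AEs are the only data that 8.6 names for it.

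What the objection does not answer is the conflict within 8.1, or the two situations in the table where the outcome rests on an undefined judgement.

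**Conclusion.** The concern holds in a limited form. Two rules in 8.1 treat worsening depression differently, and the more specific one lets an undefined judgement remove a hospital stay from AE status and therefore from SAE status. The exposed cases are prolonged stays of participants enrolled as inpatients and admissions for relapse to entry severity, possibly with suicidality, when judged neither a worsening nor more frequent.

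The size is unknown because the documents give no admission rate; each participant affected moves the SAE proportion by 5 percentage points, assuming 20 are dosed. No efficacy analysis is affected. The importance is moderate: a stated rule can make the safety result look better than it is, but existing definitions already catch clear worsening.

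**What to change.** Reconcile the two parts of 8.1 in one amendment.

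1. Limit the third exemption bullet to psychiatric stays that are ongoing or scheduled at consent and are not prolonged.
2. State that any unplanned psychiatric admission or prolonged psychiatric stay after the first infusion, and any suicidal behaviour, is recorded as an AE, and as an SAE where a criterion is met, whatever the severity at entry.
3. Assess causality afterwards on the SAE form, which already asks for the investigator's view of the association with study treatment (8.2).

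Sections 6.6 and 6.7 should also be made to agree on whether the suicide scale is given at Visits 11-16, since that bears on how well such events are picked up.

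The cost is amendment wording, a few more SAE forms and a slightly less favourable SAE count. The criteria for expedited IRB and FDA reports do not change. The amendment concerns recording and reporting only, not care.

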8.2 Recording of Adverse Events

Adverse Event Recording

At each contact with the subject, the investigator must seek information on adverse events by specific questioning and, as appropriate, by examination. Information on all adverse events will be recorded immediately in the source document, and also in the appropriate adverse event module of the case report form (CRF). All clearly related signs, symptoms, and abnormal diagnostic procedures results will be recorded in the source document, though should be grouped under one diagnosis.

All adverse events occurring during the study period must be recorded. The clinical course of each event will be followed until resolution, stabilization, or until it has been determined that the study treatment or participation is not the cause. Serious adverse events that are still ongoing at the end of the study period must be followed up to determine the final outcome. Any serious adverse event that occurs after the study period and is considered to be possibly related to the study treatment or study participation should be recorded and reported immediately.

SAE Recording

A Serious Adverse Event (SAE) form must be completed by the investigator or study team member within 24 hours of finding out about the event. The investigator must determine causality and confirm the severity of the event in the SAE form. The sponsor-investigator will keep a copy of this SAE form on file at the study site.

At the time of the initial report, the following information should be provided:

- Study identifier
- Study Center
- Subject number
- A description of the event
- Date of onset
- Current status
- Whether study treatment was discontinued
- The reason why the event is classified as serious
- Investigator assessment of the association between the event and study treatment

Within the following 48 hours, the investigator must provide further information on the serious adverse event in the form of a written narrative. This should include a copy of the completed Serious Adverse Event form, and any other diagnostic information that

will assist the understanding of the event. Significant new information of ongoing serious adverse events should be provided promptly to the sponsor-investigator.

8.3 Reporting of Serious Adverse Events

IRB Notification by Investigator

Reports of all serious adverse events (including follow-up information) must be submitted to the IRB within 10 working days if it falls under the UPIRTSO guidelines. Copies of each report and documentation of IRB notification and receipt will be kept in the regulatory binder.

Any other event not defined as an SAE, yet unanticipated, related and increases risk to subjects must be reported to the IRB within 10 working days, as defined in the IRB's UPIRTSO guidelines.

FDA Notification by Sponsor

The study sponsor shall notify the FDA by telephone or by facsimile transmission of any unexpected fatal or life-threatening experience associated with the use of the drug as soon as possible but no later than 7 calendar days from the sponsor's original receipt of the information.

If a previous adverse event that was not initially deemed reportable is later found to fit the criteria for reporting, the study sponsor will submit the adverse event in a written report to the FDA as soon as possible, but no later than 15 calendar days from the time the determination is made.

Summary Table of Reporting Requirements

| Agency | Criteria for Reporting | Timeframe | Form to Use | Submission address/fax numbers |
|----------------|--|-----------------|--------------------|--------------------------------|
| U of MN IRB | SAE : fatal, life-threatening or serious, unexpected, at least possibly related | 10 working days | UMCC SAE | |
| | UPIRTSO For all unanticipated events that | 10 working days | IRB's UPIRTSO form | MMC 820 |

CONFIDENTIAL

| | | | | |
|-----|---|------------------|--|-------------------------|
| | increase risk to subjects or others | | | |
| FDA | SAE : fatal, life-threatening, unexpected, at least possible related | 7 calendar days | FDA prefers MedWatch 3500a Form but alternative formats are acceptable (e.g. summary letter) | Fax: [name] |
| | SAE : serious, unexpected, at least possibly related | 15 calendar days | | |

8.4 Unblinding Procedures

Not applicable.

8.5 Stopping Rules

The study will be stopped if new results either from our study or from other studies arise suggesting that the risks of the study medication significantly outweigh the benefit.

8.6 Data and Safety Monitoring / Auditing

Medical Monitoring

The Principal Investigator will oversee the safety of the study at the University of Minnesota site. This safety monitoring will include careful assessment and appropriate reporting of adverse events as noted above. Medical monitoring will include a regular assessment of the number and type of serious adverse events.

Study Monitoring Plan

Independent monitoring of the clinical protocol will be conducted periodically (i.e., at a minimum of annually) by qualified staff of the UMN CTSI in accordance with the monitoring plan.

This study will be monitored according to FDA/GCP guidelines. The investigator will allocate adequate time for such monitoring activities. The Investigator will also ensure that the monitor or other compliance or quality assurance reviewer is given access to all the above noted study-related documents and study related facilities (e.g. pharmacy, diagnostic laboratory, etc.), and has adequate space to conduct the monitoring visit.

Internal Data and Safety Monitoring Board

CONFIDENTIAL

This material is the property of the University of Minnesota. Do not disclose or use except as authorized in writing by the study sponsor

An internal independent, 3-person panel of physicians and researchers will conduct a reassessment of the risks and benefits to study participants. This panel will review all adverse events for severity and frequency. [name], M.D., [name], Ph.D., and [name], M.D. will review the safety of the study after the first five participants have completed at least the first infusion. The results of their review will be submitted to the IRB. Subsequent reviews will occur annually.

Auditing and Inspecting

The investigator will permit study-related monitoring, audits, and inspections by the IRB, the sponsor, government regulatory bodies, and University compliance and quality assurance groups of all study related documents (e.g. source documents, regulatory documents, data collection instruments, study data etc.). The investigator will ensure the capability for inspections of applicable study-related facilities (e.g. pharmacy, diagnostic laboratory, etc.).

Participation as an investigator in this study implies acceptance of potential inspection by government regulatory authorities and applicable University compliance and quality assurance offices

9 Data Handling and Record Keeping

